6.5 Management for other secondary malignancies potentially promoted by vemurafenib

- 6.5.1 A thorough documented head and neck exam including a visual inspection of the mouth and lymph node palpitation will be performed by the treating physician at baseline prior to starting drug, prior to every cycle x 3, and then every 3 cycles while on therapy, and continue for 30 days after the last study treatment or until death, withdrawal of consent or lost to follow up, whichever is earlier.
- 6.5.2 A chest CT should be performed at baseline and then every 6 cycles to for a maximum of 30 days post discontinuation of study drug, death, withdrawal of consent or lost to follow up, whichever is earlier.
- 6.5.3 Abnormal findings should be evaluated as clinically indicated.

6.6 Management/dose modifications for serious hypersensitivity reactions

- 6.6.1 Severe hypersensitivity reactions including anaphylaxis have been reported in associated with vemurafenib. Severe hypersensitivity reactions include generalized rash and erythema or hypotension. In patients who experience severe hypersensitivity reaction, vemurafenib should be permanently discontinued.

6.7 Management/dose modifications for dermatologic reactions

- 6.7.1 Severe dermatologic reactions have been reported in patients receiving vemurafenib, including rare cases of Stevens-Johnson Syndrome and toxic epidermal necrolysis in the pivotal clinical trial. Drug reaction with eosinophilia and systemic symptoms syndrome (DRESS) has been reported in association with vemurafenib. In patients who experience a severe dermatologic reaction, vemurafenib should be permanently discontinued.
- 6.7.2 Patients who experience Grade \leq 3 photosensitivity/rash should be managed with supportive care. For intolerable Grade 2 or Grade \geq 3 photosensitivity, vemurafenib should be held until resolution to Grade \leq 1 and managed with dose modification per [Section 6.2](#).

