5.4.1 Non-Hematological Dose-Limiting Toxicity

5.4.1.1 Any Grade 3 or greater non-hematological toxicity attributable to the investigational drug with the specific exclusion of:

- Grade 3 nausea and vomiting of less < 3 days duration
- Grade 3 liver enzyme elevation, including ALT/AST/GGT that returns to levels that meet initial eligibility criteria or baseline within 7 days See [Appendix XII](#) for values that represent thresholds between CTCAE grades.

Note: For the purposes of this study the ULN for ALT is defined as 45 U/L regardless of baseline.

- Grade 3 or 4 fever < 5 days duration.
- Grade 3 infection < 5 days duration.
- Grade 3 hypophosphatemia, hypokalemia, hypocalcemia or hypomagnesemia responsive to supplementation
- Grade 3 rash that is tolerable

- Any Grade 2 non-hematological toxicity that is considered sufficiently medically significant or sufficiently intolerable by patients that it requires treatment interruption
- Note: Allergic reactions that necessitate discontinuation of study drug will not be considered a dose-limiting toxicity.

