6.2 Dose Modifications for Non-Hematological Toxicity

- 6.2.1 If a patient experiences non-hematological dose-limiting toxicity as defined in [Section 5.4.1](#), the treatment will be held. When the toxicity resolves to meet eligibility parameters or baseline within 14 days of drug discontinuation, the patient may resume treatment at a reduced dose as outlined in the dose reduction table (see [Appx IV-A](#) and [Appx IV-B](#)). Doses reduced for toxicity will not be re-escalated, even if there is minimal or no toxicity with the reduced dose. See specific guidelines for QTc changes, severe hypersensitivity reactions, and dermatologic reactions below.
- 6.2.2 If toxicity does not resolve to meet eligibility or baseline parameters within 14 days of drug discontinuation, the patient must be removed from protocol therapy.
- 6.2.3 Two dose reductions will be allowed for toxicity. If a patient experiences dose-limiting toxicity after two dose reductions, the patient must be removed from protocol therapy.

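### Section 6.7.2 leaves rash out of its hold sentence, although 5.4.1.1 and 6.2.1 make intolerable rash a DLT that must be held, and the protocol does not say which section governs

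*Combined protocol and SAP*

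**What the plan says.** **Section 6.7.2 (dermatologic reactions).** The first sentence covers Grade 3 and lower: "photosensitivity/rash should be managed with supportive care. For intolerable Grade 2 or Grade". The second sentence, which starts inside that quotation, continues "3 photosensitivity, vemurafenib should be held until resolution to Grade" 1 or lower, and then sends the patient to Section 6.2 for dose modification. Rash appears in the first sentence only, and that sentence carries no tolerability condition.

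**Section 5.4.1.1 (DLT definition).** The general rule is "Any Grade 3 or greater non-hematological toxicity attributable to the investigational drug with the specific exclusion of" a short list. The rash entry in that list is "Grade 3 rash that is tolerable". A further item concerns Grade 2: "Any Grade 2 non-hematological toxicity that is considered sufficiently medically significant or sufficiently intolerable by patients that it requires treatment interruption".

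**Section 6.2.1 (action on a non-hematological DLT).** "the treatment will be held. When the toxicity resolves to meet eligibility parameters or baseline within 14 days of drug discontinuation", the patient may resume at a reduced dose. It adds "Doses reduced for toxicity will not be re-escalated, even if there is minimal or no toxicity with the reduced dose", and then "See specific guidelines for QTc changes, severe hypersensitivity reactions, and dermatologic reactions below".

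**The concern.** For an intolerable Grade 3 rash attributed to vemurafenib, two parts of the protocol point different ways. The DLT definition with 6.2.1 leads to a hold and, if treatment resumes, a lower dose. The dermatology section, to which 6.2.1 itself refers the reader, leads to supportive care and mentions no hold for rash.

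A site that treats the specific section as controlling could keep a child on full dose through a rash that the protocol's own definition calls dose-limiting. What is at stake is patient management and consistency of dosing between sites. Rash is not a remote event with this drug: the adult basket study summarised in Section 2.3.2 reports it in 68% of patients, and the CAEPR lists maculo-papular rash as likely (>20%). Neither figure is a rate of intolerable Grade 3 rash.

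**Working it through.** The plan states no figure on this point. The check sets the sections side by side and then reads the dose consequence from Appendix IV.

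**Step 1. Is the event a DLT?** Grade 3 rash falls under the general rule in 5.4.1.1. The exclusion covers it only if tolerable, so intolerable Grade 3 rash stays in. I read the Grade 2 item as a separate DLT criterion although it is printed as a bullet below the exclusions: excluding a Grade 2 event from a rule that starts at Grade 3 would have no effect.

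**Step 2. What action follows under each section?**

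| Event | 5.4.1.1 with 6.2.1 | 6.7.2 read alone |
|---|---|---|
| Tolerable Grade 3 rash | Not a DLT | Supportive care |
| Intolerable Grade 3 rash | DLT: hold; restart only at reduced dose | Supportive care; no hold stated |
| Grade 2 rash intolerable enough to need interruption | DLT: hold; restart only at reduced dose | Supportive care; no hold stated |
| Grade 3 photosensitivity | DLT: hold; restart only at reduced dose | Supportive care, and hold with dose modification per 6.2 |

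The first row agrees. The second and third do not. The third is the weaker mismatch, because the Grade 2 criterion already presupposes that treatment is interrupted. There the main loss is the dose reduction.

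**Step 3. Does the text say which section governs?** No. The pointer in 6.2.1 tells the reader to see the dermatologic guidance and stops there. In the other areas it names, the specific text sets its own outcome: the QTc table in 6.3.3 has its own triggers and stopping rules, and 6.6.1 requires permanent discontinuation. Section 6.7.1 does the same for severe dermatologic reactions. A site could expect 6.7.2 to work in that way. Sections 6.8.1 and 6.9.1 send liver and eye abnormalities to 6.2 without a split of this kind. Section 6.7.1 does not settle the matter: it gives no grade, and its examples are Stevens-Johnson syndrome, toxic epidermal necrolysis and DRESS.

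**Step 4. Size for an affected patient.** Total daily dose from Appendix IV-A and IV-B, with change = (level -1 minus full) / full:

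| BSA (m²) | Full dose (mg/day) | Level -1 (mg/day) | Change |
|---|---|---|---|
| 0.55-0.72 | 240 + 480 = 720 | 240 + 240 = 480 | -240/720 = -33.3% |
| 0.73-1.09 | 480 + 480 = 960 | 240 + 480 = 720 | -240/960 = -25.0% |
| 1.1-1.53 | 720 + 720 = 1440 | 480 + 480 = 960 | -480/1440 = -33.3% |
| ≥ 1.54 | 960 + 960 = 1920 | 720 + 720 = 1440 | -480/1920 = -25.0% |

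In the smallest band, level -2 means coming off protocol therapy, so one reduction uses the only step available.

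**The case against.** The strongest reply is that there is no conflict in required action. Section 6.2.1 is mandatory once a DLT occurs, and 6.7.2 never says to continue drug. Where the protocol means that no interruption is needed, it says so, as 6.4.5 does for cutaneous squamous cell carcinoma. Grade 3 photosensitivity sits under both sentences of 6.7.2, which shows that supportive care and a hold can go together. A pointer to further guidance is also not a statement that the guidance replaces the general rule.

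Most of this stands, and it is why the additive reading is the better one. It does not remove the problem. Section 6.7.2 pairs the two events in its first sentence and then drops rash from the second, and a reader may take that as deliberate.

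Safeguards also exist. Suspected DLTs go to the Study Chair within 24 hours (5.3), each new cycle requires that Section 6.0 is met (5.2), history and physical examination are weekly in cycle 1 (8.1), and MATCH leadership reviews study data weekly (14.4.2). These make an unnoticed divergence less likely, but they do not supply the missing rule. The Section 6.0 notice to the Study Chair is triggered by a dose modification, so it is silent when a site changes nothing.

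A reader might also infer that Grade 4 rash has no rule because neither sentence of 6.7.2 reaches it. The documents do not support that. An attributable Grade 4 rash is a DLT under 5.4.1.1 and is held under 6.2.1, and 6.7.1 or 6.6.1 may require permanent discontinuation.

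**Conclusion.** The omission of rash from the hold sentence is plain on the text. It leaves 6.7.2 out of step with 5.4.1.1 and 6.2.1 for intolerable Grade 3 rash and, less sharply, for Grade 2 rash intolerable enough to require interruption. It would be too strong to say that the protocol tells sites to dose through such a rash. What the documents show is an unresolved ordering between two sections, with the hold as the better reading.

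For an affected patient the difference is full dose against a hold followed, if treatment resumes, by a daily dose 25% or 33% lower with no re-escalation. No frequency can be put on it, because the documents give neither a rate of intolerable Grade 3 rash nor any basis for how often a site would take the weaker reading.

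No effect follows for alpha, power or the decision rule of at least 3 responses in 20. This is a wording correction on a safety action, minor in scale and worth making. The conclusion assumes that the rash is attributed to vemurafenib and is not a severe reaction already covered by 6.6.1 or 6.7.1.

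**What to change.** Amend 6.7.2 in two places:

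- **First sentence:** limit supportive care alone to tolerable events, that is, tolerable rash of Grade 3 or lower and tolerable photosensitivity of Grade 2 or lower. Grade 3 photosensitivity is already in the hold sentence.
- **Second sentence:** add rash to the trigger. For photosensitivity that is intolerable at Grade 2 or is Grade 3 or higher, or for rash that is intolerable at Grade 2 or 3, hold vemurafenib until the event is Grade 1 or lower and modify the dose under Section 6.2.

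State that 6.6.1 and 6.7.1 remain in force, and make no new rule for Grade 4 rash.

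Extending the Grade 1 threshold to rash follows what 6.7.2 already does for photosensitivity. Section 6.2.1 words recovery differently (eligibility parameters or baseline, within 14 days), and Section 4 sets no grade for rash. Whether Grade 1 within 14 days is enough to restart is a clinical decision for the sponsor, which the same amendment can record.

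The cost is one reworded paragraph at the next amendment and one clinical confirmation. No new visits, procedures or patients are needed.

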6.8 Management of liver injury

- 6.8.1 Liver injury, including severe cases of liver injury has been reported with vemurafenib. Liver enzymes (transaminases and alkaline phosphatases) and bilirubin should be measured as per [Section 8.1](#). Laboratory abnormalities should be managed with dose modification per [Section 6.2](#).

6.9 Management of ophthalmologic reactions

- 6.9.1 Serious ophthalmologic reactions including uveitis have been reported with vemurafenib. Patients should be monitored for ophthalmologic reactions and any

changes may be referred to ophthalmologist. Abnormalities should be managed with dose modification per [Section 6.2](#).

7.0 SUPPORTIVE CARE AND OTHER CONCOMITANT THERAPY

7.1 Concurrent Anticancer Therapy

Concurrent cancer therapy, including chemotherapy, radiation therapy, immunotherapy, or biologic therapy may NOT be administered to patients receiving study drug. If these treatments are administered the patient will be removed from protocol therapy.

7.2 Investigational Agents

No other investigational agents may be given while the patient is on study.

7.3 Supportive Care

Appropriate antibiotics, blood products, antiemetics, fluids, electrolytes and general supportive care are to be used as necessary. Please see COG Supportive Care guidelines at <https://childrensoncologygroup.org/index.php/cog-supportive-care-guidelines>. See [Section 7.5](#) for drugs that should not be used concomitantly due to potential interactions with vemurafenib.

7.4 Growth Factors

Growth factors that support platelet or white cell number or function can only be administered for culture proven bacteremia or invasive fungal infection. The Study Chair should be notified before growth factors are initiated.

7.5 Concomitant Medications

7.5.1 CYP3A4/5 inhibitors or inducers: Moderate to strong CYP3A4/5 inhibitors and inducers are not permitted on this study and should be discontinued 14 days prior to enrollment (See [Appendix II](#) for list of agents). Note: CYP3A4 inducing anti-epileptic drugs and dexamethasone for CNS tumors or metastases, on a stable dose, are allowed.

7.5.2 Vemurafenib is a substrate for both BCRP and p-glycoprotein (p-gp). The use of known BCRP and p-gp inhibitors and inducers should be avoided for the duration of the study if reasonable alternatives exist.

Vemurafenib is also an inhibitor of BCRP, CYP1A2 (moderate), CYP2D6 (weak), P-glycoprotein and an inducer of CYP3A4 (weak). Concomitant use of vemurafenib with agents that are sensitive or narrow therapeutic range substrates of CYP1A2 and CYP3A4 is not recommended as vemurafenib may alter their concentrations. If co-administration cannot be avoided, exercise caution and consider a dose reduction of the concomitant CYP1A2 substrate drug.

Vemurafenib can increase plasma concentrations of P-gp substrates (eg., digoxin). Dose reduction of the concomitant P-gp substrate drug may be considered, if clinically indicated.

7.5.3 Co-administration of vemurafenib resulted in an 18% increase in AUC of S-warfarin (CYP2C9 substrate). Exercise caution and consider additional INR

monitoring when vemurafenib is used concomitantly with warfarin.

7.5.4 Avoid combination with other drugs with potential to lead to prolongation of QTc interval, if possible.

8.0 EVALUATIONS/MATERIAL AND DATA TO BE ACCESSIONED

8.1 Required Clinical, Laboratory and Disease Evaluation

All clinical and laboratory studies to determine eligibility must be performed within 7 days prior to enrollment unless otherwise indicated. Laboratory values used to assess eligibility (see [Section 4.0](#)) must be no older than seven (7) days at the start of therapy. Laboratory tests need **not** be repeated if therapy starts **within** seven (7) days of obtaining labs to assess eligibility. If a post-enrollment lab value is outside the limits of eligibility, or laboratory values are older than 7 days, then the following laboratory evaluations must be re-checked within 48 hours prior to initiating therapy: CBC with differential, bilirubin, ALT (SGPT) and serum creatinine. If the recheck is outside the limits of eligibility, the patient may not receive protocol therapy and will be considered off protocol therapy. Imaging studies, bone marrow aspirate and/or biopsy, must be obtained within 14 days prior to start of protocol therapy (repeat the tumor imaging if necessary).

STUDIES TO BE OBTAINED	Pre-Study	During Cycle 1	Prior to Subsequent Cycles [^]
History	X	Weekly	X
Physical Exam with vital signs	X	Weekly	X
Head and neck exam ¹	X		Every cycle x 3, and then q 3 cycles
Dermatologic Exam	X		Every cycle x 3, and then q 3 cycles ²
Height, weight, BSA	X		X
Performance Status	X		
Pregnancy Test ³	X		
CBC, differential, platelets	X	Weekly ^{4,5}	X ^{4,5}
Urinalysis	X		
Electrolytes including Ca ⁺⁺ , PO ₄ , Mg ⁺⁺	X	Weekly	X
Creatinine, ALT, bilirubin	X	Weekly	X
Albumin	X		X
EKG	X		Every cycle x 3, and then q 3 cycles
Tumor Disease Evaluation ^{6,6-A,6-B}	X		Every other cycle x 3 then q 3 cycles ⁷
Chest CT scan ⁸	X		Every 6 cycles
Bone Marrow Aspirate and/or biopsy ^{9,10}	X ¹⁰		
Medication Diary ¹¹		Weekly	X
Circulating Tumor DNA (ctDNA-optional) ¹²			Cycle 5, Day 1 and (for patients receiving ≥ 5 cycles only) at

			end of protocol therapy OR disease progression
^ Studies may be obtained within 72 hours prior to the start of the subsequent cycle unless otherwise stated.			
1	Document a thorough head and neck examination to monitor for non-cutaneous SCC. This should include a visual inspection of mouth and lymph node palpation.		
2	See section 6.4. Dermatologic exam other than baseline can be obtained within 14 days prior to cycle.		
3	Women of childbearing potential require a negative pregnancy test prior to starting treatment; sexually active patients must use an acceptable method of birth control. Abstinence is an acceptable method of birth control.		
4	If patients have Grade 4 neutropenia then CBCs should be checked at least every other day until recovery to Grade 3 or until meeting the criteria for dose limiting toxicity.		
5	If patients develop Grade 3 or greater thrombocytopenia then CBCs should be checked every 3 to 4 days until recovery per Section 6.1 .		
6	Neurological exam also required for CNS patients.		
6-A	Non- Hodgkin Lymphoma/ Histiocytosis patients are required to have PET scans within 2 weeks prior to start of therapy and should also be followed with PET scans if positive at diagnosis. Refer to Section 12.8		
6-B	Patients with neuroblastoma must have both CT/MRI and MIBG scintigraphy prior to the start of protocol therapy if the patient was enrolled with or has a history of having MIBG avid tumor. Otherwise the patient must have both CT/MRI and bone scan prior to the start of protocol therapy. For patients with neuroblastoma and measurable disease by CT or MRI, lesions should be measured and followed using the same modality (CT or MRI) in addition to MIBG or bone scan. For patients with neuroblastoma and evaluable disease by MIBG scintigraphy or bone scan, use the same modality (MIBG scintigraphy or bone scan) to image and follow patients; CT/MRI are not required but may be performed as clinically indicated. Refer to Section 12.5.4 and Section 12.9		
7	Tumor Disease Evaluation should be obtained on the next consecutive cycle after initial documentation of either a PR or CR. Subsequent scans may restart 2 cycles after the confirmatory scan. Please note that for solid tumor patients, if the institutional investigator determines that the patient has progressed based on clinical or laboratory evidence, he/she may opt not to confirm this finding radiographically.		
8	CT Chest will be performed prior to treatment and then every 6 cycles to evaluate for non-cutaneous squamous cell carcinoma. CT Chest performed as part of tumor disease assessment may be used to evaluate non-cutaneous squamous cell carcinoma.		
9	Bone marrow aspirate and/or biopsy only required in patients with known bone marrow metastasis on the basis of history, symptoms, laboratory evaluation or other clinical data.		
10	Bone marrow aspirate and/or biopsy should be performed only when complete response or partial response is identified in target disease or when progression in bone marrow is suspected.		
11	Medication diary (see Appendix III-A) should be reviewed weekly during cycle 1, after completion of each treatment cycle, and uploaded into RAVE.		
12	With consent, two samples will be collected on this protocol (cycle 5 Day 1; and for patients receiving ≥ 5 cycles only: at progression or end of protocol therapy); see Section 8.3 for details of the ctDNA studies. Note that a ctDNA sample is scheduled to be obtained on the APEC1621SC screening protocol prior to the initiation of treatment on this subprotocol.		

8.2 Radiology Studies

8.2.1 Central Radiology Review for Response:

Patients who respond (CR, PR) to therapy or have long term stable disease (SD) (≥ 6 cycles) on protocol therapy will be centrally reviewed. The Operations center will notify the site when a patient has met the criteria for review. The tumor disease evaluations to be submitted for review include baseline (pre-study) evaluations as well as all end of cycle tumor disease evaluations which occurred while the patient was on the subprotocol therapy study.

8.2.2 Technical Details of Submission:

To ensure an adequate interpretation of FDG-PET and CT with contrast scans, scans transferred between the treating institutions and the Imaging and Radiation Oncology Core Group IROC RI (QARC) must be submitted in Digital Imaging and Communications in Medicine (DICOM) format. BMP files, JPG files, or hard copies (films) are unacceptable for adequate interpretation of PET and CT with contrast scans. Imaging studies must be submitted electronically as outlined in the following paragraph. The images will be made available to study radiologists and nuclear medicine physicians for central review.

Submission of Diagnostic Imaging data in DICOM format is required. Submission of the digital files and reports via TRIAD is preferred. Instructions for TRIAD set up are below.

Alternatively, the images and reports may be submitted via sFTP to IROC Rhode Island. Digital data submission instructions including instructions for obtaining a sFTP account, can be found at <http://irocri.qarc.org>. Follow the link labeled digital data. Sites using the Dicommunicator software to submit imaging may continue to use that application.

Corresponding Radiology reports may be submitted along with the electronic submission via TRIAD or sFTP or may be emailed to [contact]. The COG operations center and IROC are available to assist with any queries regarding the corresponding radiology reports which should be included when the scans are submitted

Questions may be directed to [contact] or [contact].

Digital RT Data Submission Using TRIAD (if TRIAD is available at your site):
TRIAD is the American College of Radiology's (ACR) image exchange application. TRIAD provides sites participating in clinical trials a secure method to transmit DICOM and DICOM RT files and other digital objects, such as reports. TRIAD de-identifies and validates the images as they are transferred.

TRIAD Access Requirements:

Site physics staff who will submit images through TRIAD will need to be registered with the Cancer Therapy Evaluation Program (CTEP) and have a valid and active CTEP Identity and Access Management (IAM) account. Please refer to CTEP Registration Procedures of the protocol for instructions on how to request a CTEP-IAM account.

To submit images, the site TRIAD user must be on the site roster and be assigned the 'TRIAD site user' role on the CTSU roster. Users should contact the site's CTSU Administrator or Data Administrator to request assignment of the TRIAD site user role.

TRIAD Installations:

When a user applies for a CTEP-IAM account with the proper user role, he/she will need to have the TRIAD application installed on his/her workstation to be able to submit images. TRIAD installation documentation can be found by following this link <https://triadinstall.acr.org/triadclient/>

This process can be done in parallel to obtaining your CTEP-IAM account username and password.

If you have any questions regarding this information, please send an e-mail to the TRIAD Support mailbox at [contact].

IROC Rhode Island (formerly QARC) will facilitate the central reviews.

For FDG-PET imaging, the transferred imaging data should include uncorrected and attenuation-corrected PET projection data, as well as the reconstructed PET or PET/CT images used by the institution to achieve a response assessment. If low-dose CT was used for attenuation correction, the acquired CT images should also be submitted. The imaging data submitted for central review must allow the study to be reconstructed and displayed in transaxial, sagittal and coronal formats using standard reconstruction techniques. Reconstructed MPEG clips and similar types of reconstructions will not be accepted. CT and MRI images similarly should be submitted in a format that either includes properly reconstructed multi-planar viewing formats in soft tissue and bone windows, or includes the thin-section axial acquisition data from which multi-planar reconstructions can be re-created.

Sites not able to submit imaging electronically may submit imaging via CD. CD's may be sent by courier to:

Address for submission: IROC RI (QARC)
[name]
[name]
[name]
[contact]
[contact]
Web: <http://irocri.qarc.org>

